### 3.5.2. Laboratory Data

The following laboratory tests will be reported:

**Table 2. Clinical Laboratory Tests**

Clinical Chemistry Panel	Hematology Panel	Urinalysis	Lipid Panel

 
• Sodium
 
• Potassium
 
• Chloride
 
• Bicarbonate
 
• Total protein
 
• Albumin
 
• Calcium
 
• Magnesium
 
• Glucose
 
• BUN
 
• Creatinine
 
• eGFR based on CKD-Epi
 
• Uric acid
 
• Total bilirubin
 
• Direct (conjugated) bilirubin
 
• Indirect (unconjugated) bilirubin
 
• AST
 
• ALT
 
• Alkaline phosphatase
 
	
 
• Red blood cells
 
• Hemoglobin
 
• Hematocrit
 
• MCV, MCH, MCHC
 
• Platelets
 
• WBC differential (% and absolute)
 
• Neutrophils
 
• Eosinophils
 
• Basophils
 
• Lymphocytes
 
• Monocytes
 
	
 
• Routine urinalysis 
 
- Color
 
- Appearance
 
- Specific gravity
 
- pH
 
- Protein
 
- RBC
 
- Glucose
 
- Ketones
 
- Bilirubin
 
- Urobilinogen
 
- Leukocyte esterase
 
- Nitrate
 
 
 
• Microscopic examination (reflex testing based on urinalysis results)
 
• A/C ratio (UACR)
 
	
 
• Total cholesterol
 
• LDL cholesterol – direct measurement
 
• HDL cholesterol
 
• Non-HDL cholesterol
 
• Triglycerides
 
• VLDL cholesterol – direct measurement
 

Extended Lipoprotein Panel, FFA	Coagulation	Pharmacokinetics	Immunogenicity

 
• Lp(a)
 
• ApoB
 
• ApoB-48
 
• ApoB-100
 
• ApoC-III
 
• ApoA-I
 
• FFA
 
	
 
• aPTT (sec)
 
• PT (sec)
 
• INR
 
	
 
• PF-07285557 concentration in plasma
 
	
 
• Anti-PF-07285557 antibodies
 

PD	Inflammatory	Other	

 
• ANGPTL3
 
	
 
• hsCRP
 
	
 
• FSHa
 
• Pregnancy test (β-hCG), urine and serumb
 
• HbA1c
 
	

a. For confirmation of postmenopausal status only.

b. For female participants of childbearing potential.

#### 4. ANALYSIS SETS (POPULATIONS FOR ANALYSIS)

Data for all participants will be assessed to determine if participants meet the criteria for inclusion in each analysis population prior to unblinding and releasing the database and classifications will be documented per standard operating procedures.

Participant Analysis Set	Description
Enrolled/Randomly assigned to study intervention (All Subjects Randomized)	"Enrolled" means a participant's, or their legally authorized representative's, agreement to participate in a clinical study following completion of the informed consent process. Potential participants who are screened for the purpose of determining eligibility for the study, but do not participate in the study, are not considered enrolled.
Evaluable	All participants randomly assigned to study intervention and who take at least 1 dose of study intervention. Participants will be analyzed according to the randomized intervention.
Safety	All participants randomly assigned to study intervention and who take at least 1 dose of study intervention. Participants will be analyzed according to the treatment group they are randomized to unless the wrong study intervention is received throughout the study.

##### 4.1. Full Analysis Set

The Full Analysis set (FAS) is defined as subjects in the "Evaluable" population who have a baseline measurement and at least one post-baseline measurement. Furthermore, FAS\_primary is defined as FAS with all observations that occur after discontinuation of treatment or after initiation of severe hypertriglyceridemia (Section 8.2.7. of protocol) excluded. FAS\_primary will be the primary analysis set for the analysis of primary, secondary endpoints and tertiary/exploratory endpoints. FAS serves as the analysis set for supplementary analyses corresponding to the TP estimand.

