### 1.3. Schedule of Activities (SoA)

The SoA table provides an overview of the protocol visits and procedures. Refer to the [STUDY ASSESSMENTS AND PROCEDURES](#) section of the protocol for detailed information on each procedure and assessment required for compliance with the protocol. The investigator may schedule visits (unplanned visits) in addition to those listed in the SoA table, in order to conduct evaluations or assessments required to protect the well-being of the participant. In the event of a health care crisis, pandemic, or other emergency, some of the assessments may be performed via home health visits or other ways after discussion with the sponsor. See [Appendix 13](#) for alternative measures that may be allowed during a public emergency, such as COVID-19.

Visit Identifier a Abbreviations used in this table may be found in Appendix 14 .	Screening b (Days -28 to -1)			Day 1	Day 8	Day 15	Day 29	Day 43	Day 57	Day 85	Day 113 Interim Analysis Time Point	Day 141	Day 169	Follow-up (+12 weeks after last dose) c,f	Early Termination/ Discontinuation g
	Visit 1 c,d	Visit 2	Visit 3												
Week	-4 to -1			0	1	2	4	6	8	12	16	20	24	32 or 34	
Month	-1						1		2	3	4	5	6	8	
Visit Window (Days)					±1	±1	±2	±2	±2	±3	±3	±3	±3	±7	
Informed consent	X														
Medical history	X														
Inclusion/Exclusion Criteria	X			X											
Physical examination	X														
Vital signs (seated blood pressure and pulse rate)	X			X							X		X		X
Weight	X			X									X		X
Height	X														
Provide contact card to participant	X														
Dispense diary and instruct participant on use				X h											
Laboratory															
Hematology	X			X	X i	X	X	X	X	X	X	X	X	X	X
Blood chemistry	X			X	X i	X	X	X	X	X	X	X	X	X	X
Lipid panel and ApoB j	X			X			X		X	X	X	X	X	X	X
Extended lipoprotein panel and FFA k				X									X		X
ANGPTL3 l				X			X		X	X	X	X	X		X
HbA1c	X			X									X	X	X

Visit Identifier a Abbreviations used in this table may be found in Appendix 14 .	Screening b (Days -28 to -1)			Day 1	Day 8	Day 15	Day 29	Day 43	Day 57	Day 85	Day 113 Interim Analysis Time Point	Day 141	Day 169	Follow-up (+12 weeks after last dose) c,f	Early Termination/Discontinuation g
	Visit 1 c,d	Visit 2	Visit 3												

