Month	-1						1		2	3	4	5	6	8	
Visit Window (Days)					±1	±1	±2	±2	±2	±3	±3	±3	±3	±7	

- a. Day relative to start of study intervention (Day 1).
- b. Screening Period is a maximum of 28 days. Complete all inclusion/exclusion procedures and assessments denoted at Screening Visit 1; placebo injection training may be performed at Screening Visit 1 or Screening Visit 2. After participant has otherwise qualified for the study, including review of lipid and clinical laboratory results and completion of successful placebo training injections, perform MRI-PDFF at Screening Visit 3 or any time prior to randomization.
- c. If participants are not fasted for lipid panel and ApoB collection, perform other Screening activities and have participants return fasted for these tests.
- d. Screening Visit 1 activities should be completed within 7 days.
- e. Occurs 12 weeks after last dose: Week 32 for participants assigned to Q4W regimen or Week 34 for participants assigned to Q2W regimen.
- f. For participants who discontinue the study after Week 24, perform Follow-up procedures; do not perform Early Termination/Discontinuation procedures.
- g. For participants who discontinue study intervention or discontinue the study prior to Week 24, the procedures should be performed. Early Termination/Discontinuation procedures to be performed *as soon as practically possible* after decision to stop study intervention but participants should stay in study with continuation of scheduled visits unless participant withdraws consent from further study participation.
- h. Diary to be dispensed only to participants assigned to Q2W regimen.
- i. Laboratory results from Week 1 visit should be reviewed by the investigator prior to Week 2 dosing for participants dosing Q2W and prior to Week 4 dosing for participants dosing Q4W.
- j. Lipid panel and ApoB should be obtained with participants in a fasted state ([Section 5.3.2](#)). Lipid panel includes non-HDL-C, TG, direct LDL-C, total cholesterol, HDL-C, direct VLDL-C.
- k. Extended lipoprotein panel and FFA should be obtained with participants in a fasted state ([Section 5.3.2](#)). Extended lipoprotein panel includes Lp(a), ApoB-48, ApoB-100, ApoC-III, ApoA-I.
- l. ANGPTL3 should be obtained with participants in a fasted state ([Section 5.3.2](#) and [Section 8.6](#)).

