#### **5.3.2. Dietary Restrictions and Fasting**

Participants should maintain their usual diet and exercise regimen throughout the study.

Participants should abstain from all food and drink (except water) for  $\geq 10$  hours prior to Screening Visit 1 and visits at Weeks 0, 4, 8, 12, 16, 20, 24, follow-up, and Early Termination/Discontinuation visit (if applicable) for testing of lipids, extended lipoprotein panel, FFA, ANGPTL3, hsCRP, or PK. Prior to the visit, the study site should contact the participant to remind him/her of the fasting requirement and specify the time the participant should stop eating relative to the time of the visit. Participants are permitted to take concomitant medications (provided that they can be taken in the fasting state), taken as prescribed with water, on the morning of a study visit.

Participants must abstain from all food and drink (except water) for  $\geq 4$  hours prior to MRI-PDF assessment.

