### 9.3. Analysis Set

For purposes of analysis, the following analysis sets are defined:

Participant Analysis Set	Description
Enrolled/Randomly assigned to study intervention	"Enrolled" means a participant's, or their legally authorized representative's, agreement to participate in a clinical study following completion of the informed consent process. Potential participants who are screened for the purpose of determining eligibility for the study, but do not participate in the study, are not considered enrolled.

Evaluable	All participants who are randomized, take at least 1 dose of study intervention and have baseline measurements and at least 1 post-baseline measurement.
Safety	All participants randomly assigned to study intervention and who take at least 1 dose of study intervention. Participants will be analyzed according to the treatment group they are randomized to unless the wrong study intervention is received throughout the study.

Defined Analysis Set	Description
FAS_Primary	In the evaluable analysis set, for participants who discontinue treatment, all post-discontinuation observations will be censored to missing.
FAS	In the evaluable analysis set, for participants who discontinue treatment, all observations post-discontinuation will be included in the analysis set.

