### 2.1.3. Additional Estimand(s)

#### Estimands of supplementary analyses

In many settings due to intolerance or inadherence, such as discontinuation of treatment or initiation of an add-on therapy when pre-specified criteria are met, including all data collected in the analysis will violate the assumption of the hypothetical estimand.

Following the estimand theory, as detailed in [1], the following two additional estimands will be used for supplemental analyses of primary and key secondary endpoints (ie, at Week 24). The treatment policy estimand estimates the between-group difference of treatment effect without regard to tolerance or adherence to the randomized treatment (eg, receipt of treatment for severe hypertriglyceridemia). The principal stratum

estimand estimates the between-group difference of treatment effect, restricted to the stratum that subjects who adhere to their randomized vupanorsen groups, but regardless of adherence to the placebo group (ie,  $S_{*+}$  in [2]).

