### 5.3. Methods to Manage Missing Data

The missing data of the primary hypothetical estimand are defined as all visits post occurrence of intercurrent events (Section 2.1.1). In the primary analysis, due to its inherent assumption of missing at random (MAR), no explicit imputation is needed. The following return to baseline (RTB) sensitivity analysis will be conducted to further evaluate the robustness of the primary results, by using a specific MNAR assumption to impute the missing data of Week 24. Then we will introduce the MI-RD supplementary analysis, as it's the only approach that explicitly imputes missing data, out of all three supplementary analyses.

The RTB missing data sensitivity analysis will be implemented on the same analysis set and hypothetical estimand as the primary analysis, but with a varied assumption, to assess how robust the primary results are. The RTB approach assumes for subjects with missing values at Week 24, their values at Week 24 should eventually return to around their baseline level, ie, their values at Week 24 will be imputed using a normal distribution with the baseline level as the mean and the mean squared error (MSE) from ANCOVA model excluding subjects with missing Week 24 values as the variance. A total of 100 imputations will be performed and each dataset will be analyzed using ANCOVA adjusting for baseline value and treatment group (categorical), then all 100 results will be combined into a single estimate following Rubin's rules [3].

The MI-RD approach serves as additional evaluation of the primary results, along with the other two supplementary analyses. It defines missing data differently, due to the TP estimand it represents. More specifically, it includes data collected post occurrence of intercurrent events in the analysis, and therefore its missing data scope is smaller than the hypothetical estimand. This approach assumes subjects who discontinue the study are expected to have similar values of endpoints, compared to those in the same treatment group that agree to stay in the study for safety follow-up after treatment discontinuation ("retrieved dropouts"), after adjusting for values of baseline visit and last on-treatment visits. The imputation is implemented within groups defined by treatment groups. The missing values at Week 24 are imputed with baseline, last on-treatment visit as predictors, using a regression-based MI approach. The imputation dataset only contains

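### If the Full Analysis Set requires a post-baseline lipid value, the return-to-baseline analysis omits the earliest dropouts, although it needs only their baseline value

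*SAP*

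**What the plan says.** SAP 4.1 builds FAS from dosed participants "who have a baseline measurement and at least one post-baseline measurement". FAS_primary is FAS with observations removed after treatment stops or after treatment for severe hypertriglyceridemia starts. Protocol 9.3 puts the same condition one level higher: participants enter its Evaluable set only if they "have baseline measurements and at least 1 post-baseline measurement". The SAP's Evaluable set (section 4) requires only randomization and one dose. Neither document says which measurement counts.

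In the Schedule of Activities (Protocol 1.3), the row "Lipid panel and ApoB" is sampled at Screening and Day 1 and next at Day 29. Protocol 5.3.2 agrees, asking for fasting before "visits at Weeks 0, 4, 8, 12, 16, 20, 24, follow-up, and Early Termination/Discontinuation visit (if applicable) for testing of lipids". ANGPTL3 is also first re-measured at Day 29. Safety laboratory tests resume on Day 8.

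Two provisions limit early loss. On Early Termination, Protocol 1.3 says: "For participants who discontinue study intervention or discontinue the study prior to Week 24, the procedures should be performed". That visit includes lipids, ApoB and ANGPTL3. It adds that "participants should stay in study with continuation of scheduled visits unless participant withdraws consent from further study participation".

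SAP 5.3 describes RTB as assuming that "for subjects with missing values at Week 24, their values at Week 24 should eventually return to around their baseline level". It places RTB on the primary analysis set, and Appendix 1 lists FAS_primary, but SAP 6.1.1.2 says FAS. MI-RD runs on FAS and uses baseline and the last on-treatment visit as predictors. SAP 2.1.3 describes the treatment-policy estimand as "without regard to tolerance or adherence to the randomized treatment".

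**The concern.** RTB exists to show how far the primary result depends on treating dropouts as missing at random. It draws each missing Week 24 value around the participant's own baseline, so it needs nothing measured after dosing. A set that requires a post-baseline lipid removes exactly those who left before providing one. Each of them would have been imputed at about zero change, so removing them from a vupanorsen arm makes the RTB result look closer to the primary result than it should.

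MI-RD has the same gap. It is the only treatment-policy analysis that imputes, and it would be conditional on staying long enough to give a sample. The study is for estimation and dose selection. If early loss differs between arms, the distortion differs between arms too.

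**Working it through.** **Inputs.** From Protocol 9.2: SD 17.5, 15% treatment discontinuation, 20 per arm, difference -20, two-sided alpha 0.05. From Protocol 4.3: a 35% mean reduction, the modelled target for the top dose, used here as a second scenario. Assumed: placebo mean change 0; all 15% have no usable Week 24 value; a share e of the arm, anywhere from 0 to 15%, has no post-baseline lipid.

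**Plan's own figures.** The number remaining is 20 × 0.85 = 17. The half-width is 1.96 × 17.5 × √(2/17) = 11.76. Power for a difference of -20 is 91.5%. Both figures reproduce.

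**RTB shift.** With true effect D and missing share m:
- All dosed participants: D × (1 − m).
- FAS only: D × (1 − m)/(1 − e).

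For one early loss among three missing in an arm of 20, the multipliers are 17/20 = 0.850 and 17/19 = 0.895.

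| e | D = -20: all dosed / FAS / gap | D = -35: all dosed / FAS / gap |
|---|---|---|
| 2.5% | -17.0 / -17.4 / 0.4 | -29.75 / -30.5 / 0.8 |
| 5% | -17.0 / -17.9 / 0.9 | -29.75 / -31.3 / 1.6 |
| 10% | -17.0 / -18.9 / 1.9 | -29.75 / -33.1 / 3.3 |
| 15% (ceiling) | -17.0 / -20.0 / 3.0 | -29.75 / -35.0 / 5.25 |

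At D = -20 the full RTB penalty is 20.0 − 17.0 = 3.0 points. One early loss in 20 hides 0.89/3.0 = 30% of it.

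**Simulation check.** The set-up was 20 active against 40 placebo, with 3 and 6 missing, 20 imputations combined by Rubin's rules, 2000 runs and no baseline covariate. Omitting 0, 1, 2 or 3 of the missing active participants, and twice as many placebo participants, gave mean RTB estimates of -16.9, -17.9, -18.7 and -20.0. This agrees with the formula.

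**MMRM.** A participant with no post-baseline response contributes no rows. In one simulated data set, a random-intercept repeated-measures model was fitted with and without three baseline-only participants. Both fits used the same 342 rows and 57 participants and gave the same Week 24 difference (-28.996).

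**MI-RD.** Day 1 lipids are taken before the injection (Schedule of Activities, note u) and are averaged into baseline (SAP 3.4). These participants therefore have no on-treatment value, and the MI-RD model as written lacks a predictor for them. No MI-RD shift was calculated.

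**The case against.** A reader might infer that everyone lost before Week 4 disappears. The documents do not support that. An Early Termination visit with lipids is expected at any stop before Week 24, and those who only stop treatment are asked to keep attending. The exclusion is certain only for those who leave the study with neither sample. Some will do so: consent can be withdrawn, and Protocol 7.2.1 does not treat missed termination procedures as a deviation if safety was preserved. An Early Termination lipid on Days 2 to 14 is also uncertain, because it falls in no reporting window (the Week 4 window in SAP Appendix 2.1 opens on Day 15).

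If any assessment counts as a measurement, a Day 8 safety test admits the participant and RTB imputes the missing value. That is a fair reading. It means the wording supports two different populations, which is itself a reason to define the term.

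It is also tempting to say that the omission always favours vupanorsen. It does not. Suppose placebo completers average -5 and only placebo loses people early (2 of 40, with 6 missing in all). The placebo RTB mean moves from -5 × 34/40 = -4.25 to -5 × 34/38 = -4.47, and vupanorsen's advantage shrinks by 0.22 points.

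Finally, RTB is deliberately run on the primary set so that only the missing-data assumption changes. Widening the set does not break that match, because baseline-only participants add nothing to the MMRM. It is true, however, that SAP 5.1 plans no formal decision rule, that the primary result is untouched, and that MI-RD may not be produced if retrieved dropouts are too few.

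**Conclusion.** The point holds for RTB and, if it is produced, for MI-RD, on the reading that the qualifying measurement is the endpoint. At the sizing effect of -20 with 15% missing, the RTB overstatement is about 0.4 to 0.9 points if 2.5% to 5% of a vupanorsen arm has no post-baseline lipid. The ceiling of 3.0 points is reached only if all 15% leave that early. This is small against a half-width of 11.76. It is nevertheless systematic, and it can remove a noticeable part of the penalty that RTB is meant to show.

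The size rests on a placebo change near zero and on an early-loss share that the documents do not give. The 15% is a rate of stopping treatment, not of leaving without a sample. The documents also give no early-dropout rates by dose, so a dose-related distortion is possible but not shown.

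A reader might extend the criticism to the treatment-policy analyses as a whole. That fails for the treatment-policy MMRM, which, like the primary MMRM, gives the same answer with or without these participants.

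**What to change.** In SAP 4.1, 5.3, 6.1.1.2 and Appendix 1:
- Run RTB on all randomized participants who took at least one dose and have a baseline value of the endpoint, imputing Week 24 for anyone without a usable value. Spell the set out rather than calling it Evaluable, which the protocol and the SAP define differently. This also settles whether RTB uses FAS_primary or FAS.
- If MI-RD is produced, use the same set and state that baseline stands in for the last on-treatment value when there is none.
- Define the post-baseline measurement in SAP 4.1 by endpoint, and say how Early Termination samples map to visits.
- Report by arm the number of dosed participants with no post-baseline lipid value.

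Keep FAS_primary for the primary MMRM. The cost is SAP wording, a few more imputed rows and possibly slightly less favourable RTB estimates.

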##### 4.2. Safety Analysis Set

The safety analysis set is defined as subjects in the "Safety" population, ie, randomized subjects who have taken at least one dose of study intervention. They will be analyzed according to their randomized treatment, unless the incorrect treatment is received throughout the study, in which case they will be analyzed according to the treatment received.

##### 4.3. PK/PD Analysis Set

The PK/PD analysis set includes all randomized subjects with at least one PK or PD sample.

#### 4.4. Other Analysis Sets

FAS\_ps will be the analysis set for supplementary analyses using the principal stratum estimand (Section 2.1.3.2). The set is defined differently in vupanorsen groups vs placebo group. For vupanorsen groups, this set consists of FAS subjects who adhere to the randomized treatment group with no occurrence of intercurrent events. In other words, subjects who prematurely discontinue treatment or are assigned additional medication for treatment of severe hypertriglyceridemia prior to Week 24 will be excluded from this set. However, for the placebo group, the set is simply the FAS restricted to the placebo group, regardless of treatment adherence.

### 5. GENERAL METHODOLOGY AND CONVENTIONS

The primary analysis will be performed when all subjects have finished the visit of Week 24 or have prematurely discontinued the study prior to Week 24. Although this study has an additional 12-week safety follow-up period, the data collected until Week 24 constitutes the efficacy part of this study. Therefore, the sponsor will be unblinded and efficacy and safety results will be reported after this milestone is reached. Additional observations that occur after Week 24 will be reported after the 12-week safety follow-up is completed.

